## 5 Planned Analyses

### 5.1 Methodological Considerations

The study will be conducted under the same protocol across all the sites. No formal statistical analyses are planned to evaluate the consistency of efficacy results across the multiple clinical sites. These results, however, will be tabulated and if a site's efficacy data are obviously inconsistent with the results across all sites, this will be explored and addressed in the final study report.

Two-sided hypothesis testing will be conducted for all the tests. Resulting p-values less than 0.05 will be considered statistically significant unless noted otherwise. No adjustments of p-values for multiple comparisons will be made. No interim analyses are planned. SAS software will be used for all data analyses and tabulations.

### 5.2 Handling of Dropouts or Missing Data

[REDACTED]

For demographic and baseline characteristics and the safety profile, each variable will be analyzed using all available data. Subjects with missing data will be excluded only from the analyses for which data are not available.

### 5.3 Demographics and Baseline Characteristics

Baseline variables (e.g., sex, age, ethnic origin) will be evaluated, adjusting for site, to identify differences between treatment groups, which were not eliminated by randomization. Any significant baseline differences will be reviewed for their potential impact on the efficacy findings.

Continuous variables at baseline will be examined by two-way analysis of variance (ANOVA) with treatment and site as fixed effects when normal error and homogeneous variance assumptions are satisfied, or by the nonparametric rank based ANOVA when they are not, to compare treatment group differences.

Categorical variables such as gender, race, etc., will be examined by Cochran-Mantel-Haenszel test, stratified by site.

Summary tables by treatment group will be presented. For each continuous variable, the summary will include the mean, standard deviation, minimum and maximum. For each categorical variable, the summary will include frequencies and percentages.

### 5.4 Subject Accountability

A summary of subject disposition will be provided for all subjects. Descriptive summaries of subject disposition, reason for discontinuation, and analyses population will be provided by treatment group. The data will also be presented in subject data listings.

## 5.5 Efficacy Variables and Analyses

### 5.5.1 Primary Endpoints

The primary efficacy endpoints for the study are the mean percent change from baseline to Week 12 (Visit 4/Day 84) in the inflammatory (papules and pustules) lesion counts AND the mean percent change from baseline to Week 12 (Visit 4/Day 84) in the non-inflammatory (open and closed) lesion counts.

#### Equivalent Efficacy

For the mean percent change from baseline in the inflammatory lesion counts, the Test treatment will be considered to be therapeutically equivalent to the Reference treatment if the 90% confidence interval on the Test-to-Reference ratio of means, calculated by Fieller's Method, falls within the interval 0.80 to 1.25. The compound hypothesis to be tested for therapeutic equivalence between test and reference is:

$$H_0: \mu_T / \mu_R \leq 0.80 \text{ or } \mu_T / \mu_R \geq 1.25 \text{ versus}$$

$$H_A: 0.80 < \mu_T / \mu_R < 1.25.$$

Where  $\mu_T$  and  $\mu_R$  are the mean percent change from baseline to Week 12 (Visit 4/Day 84) in inflammatory lesions counts for the test treatment and the reference treatments, respectively. The null hypothesis is rejected when the two-sided 90% confidence interval (CI) for the ratio of means between test and reference products is between 0.80 and 1.25. Rejection of the null hypothesis supports the conclusion of therapeutic equivalence between test and reference products for the primary efficacy variable.

The two-sided 90% confidence interval will be constructed using an ANOVA model adjusting for the effects of treatment and site. A skewness test (SAS® PROC UNIVARIATE) will be performed using the residuals from the ANOVA of the primary efficacy variable. If the skewness statistic is less than -2, the analysis will be performed on the ranked mean percent change from baseline to Week 12 (Visit 4/Day 84) in inflammatory lesion counts.

The same analysis will be applied to the mean percent change from baseline in the non-inflammatory lesion count.

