8.1.2 Planned Analysis

All randomized subjects who received study medication will be evaluated for safety. The efficacy analysis will be conducted on both the PP and the mITT subject populations. Two-sided hypothesis testing will be conducted for tests. Resulting p-values less than or equal to 0.05 will be considered statistically significant. No adjustments of p-values for multiple comparisons will be made. No interim analyses are planned. SAS software will be used for all data analyses and tabulations.

The treatment response will be summarized by treatment group for the end-of-treatment evaluation. The two primary efficacy endpoints will be the mean percent change from baseline to Week 12 in the inflammatory (papules and pustules) lesion counts AND the mean percent change from baseline to Week 12 in the non-inflammatory (open and closed) lesions.

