8.1.4 Efficacy Measures and Analysis

Clinical endpoints

The primary efficacy measure will be the mean percent change from baseline to Week 12 in the inflammatory (papules and pustules) lesion counts AND the mean percent change from baseline to Week 12 in the non-inflammatory (open and closed) lesion counts. The secondary efficacy measure will be the proportion of subjects with clinical success on the Investigator's Global Assessment (IGA) at Week 12. Success is defined as an IGA score that is at least 2 grades less than the baseline assessment.

Equivalent efficacy

For the mean percent reduction from baseline in the inflammatory and non-inflammatory lesion counts, the Test treatment will be considered to be therapeutically equivalent to the Reference treatment if the 90% confidence interval on the Test-to-Reference ratio of means, calculated by Fieller's Method, falls within the interval 0.80 to 1.25. The treatment means and estimate of residual variance for the confidence interval calculation will come from an Analysis of Variance of the Test and Reference results using a statistical model containing terms for Treatment and Center.

For the proportion of subjects with clinical success, the Test treatment will be considered to be therapeutically equivalent to the Reference treatment if the 90% confidence interval on the difference between Test and the Reference proportions is contained within the interval -20% to +20%. The confidence interval will be constructed using Wald's method with Yates' continuity correction.

[REDACTED]

Superiority

For the percent reductions from baseline in the inflammatory and non-inflammatory lesion counts, each active treatment will be evaluated to determine if it has superior efficacy to that of the Vehicle at Visit 4/Week 12 via an Analysis of Variance using a statistical model containing terms for Treatment and Center.

The proportion of subjects with clinical success for each active treatment will be compared to that of the Vehicle using a Z-test with Yates' continuity correction.

All hypothesis tests will be two-sided at a significance level of $\alpha = 0.05$, except confidence intervals which will be based on $\alpha = 0.1$ (i.e. 90% coverage). [REDACTED]

[REDACTED]

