#### Superiority

Evaluation of superiority will be conducted separately for the Test versus Placebo products and for the Reference versus Placebo products comparing their difference in the percent change from baseline in the inflammatory lesion counts using ANOVA with treatment and site as fixed effects. If the mean percent change for an active treatment is greater and statistically different (two-sided,  $p < 0.05$ ) than that of the Placebo, then the active treatment will be considered superior to the Placebo. The compound hypothesis to be tested for superiority of test and reference over Vehicle is:

$H_0: \mu_T \leq \mu_V$  or  $\mu_R \leq \mu_V$  versus

$H_A: \mu_T > \mu_V$  and  $\mu_R > \mu_V$

Where  $\mu_T$ ,  $\mu_R$  and  $\mu_V$  are the mean percent change from baseline to Week 12 (Visit 4/Day 84) in inflammatory lesions counts for the test, the reference and the vehicle treatments, respectively.

. The null hypothesis is rejected when both p-values from the ANOVA are less than 0.05 (two-sided test). Rejection of the null hypothesis supports the conclusion of superiority of active product over the vehicle product for the primary efficacy variable.

[REDACTED]

The same analysis will be applied to the mean percent change from baseline in the non-inflammatory lesion count.

[REDACTED]

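### If residual skewness falls below -2, both co-primary equivalence analyses switch to ranks with no rank-scale estimand or margin, so the stated 0.80 to 1.25 ratio of mean percent changes is no longer what is tested

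*SAP*

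**What the plan says.** SAP 5.5.1 (Equivalent Efficacy) declares equivalence when "the 90% confidence interval on the Test-to-Reference ratio of means, calculated by Fieller's Method, falls within the interval 0.80 to 1.25". The two means in the hypotheses "are the mean percent change from baseline to Week 12 (Visit 4/Day 84) in inflammatory lesions counts for the test treatment" and for the reference. They are means on the percent scale, not mean ranks.

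The SAP then calls for a skewness check on the ANOVA residuals and adds: "If the skewness statistic is less than -2, the analysis will be performed on the ranked mean percent change". The section extends the procedure to the second co-primary endpoint: "The same analysis will be applied to the mean percent change from baseline in the non-inflammatory lesion count".

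Protocol 8.1.4 states the same ratio criterion, opening "For the mean percent reduction from baseline in the inflammatory and non-inflammatory lesion counts". The means and residual variance "will come from an Analysis of Variance of the Test and Reference results using a statistical model containing terms for Treatment and Center". Its visible text has no rank step. Protocol 8.1.2 adds: "The efficacy analysis will be conducted on both the PP and the mITT subject populations".

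**The concern.** An equivalence margin has meaning only in the units of the quantity it bounds. Ranks are a familiar fallback for a superiority test, where the null hypothesis is no difference. Here the null hypothesis is a ratio of 0.80 or 1.25 on the percent scale, and ranking removes that scale. The SAP does not say what the rank analysis estimates, whether Fieller's method still applies, or which limits decide.

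The trigger also looks in a plausible direction. Protocol 8.1.4 speaks of percent reduction. The SAP's Superiority text treats a larger value as better: "If the mean percent change for an active treatment is greater and statistically different". Coded that way, the response is capped at 100% improvement and has a long tail towards worsening, which is negative skewness.

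At stake is the pass/fail decision on both co-primary endpoints. Once the switch fires, a product at the 0.80 limit may pass, or one well inside the limits may fail, depending on the shape and spread of the data.

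**Working it through.** **Inputs from the documents.** Ratio of mean percent changes; Fieller 90% interval (one-sided level 0.05 at each limit); limits 0.80 and 1.25; switch at residual skewness below -2. The documents show no sample size, power or SD, so there is no planning figure to reproduce.

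**Step 1: what the limits mean on ranks.** Rank Test and Reference together, with equal arms and large samples. Let P be the chance that a Test subject has a larger reduction than a Reference subject. Then

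ratio of mean ranks = (0.5 + P) / (1.5 - P).

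- Lower limit: P = (0.80 × 1.5 - 0.5) / 1.80 = 0.389.
- Upper limit: P = (1.25 × 1.5 - 0.5) / 2.25 = 0.611.

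The carried-over test is therefore 0.389 < P < 0.611. It contains no mean percent change.

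**Step 2: two hand examples** (assumed: percent reduction = 100 - remaining %, remaining % lognormal, CV 0.8 for Reference).

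- *Looser.* Reference mean reduction 45% (55% remaining). Test at a true ratio of 0.80 has 36% (64% remaining), same CV. Log-scale SD = √ln(1 + 0.8²) = 0.703. P = Φ(-ln(64/55) / (0.703 × √2)) = 0.4395. Rank ratio = 0.9395 / 1.0605 = 0.886. A product exactly on the stated limit lies well inside the rank limits.
- *Stricter.* Reference mean reduction 65% (35% remaining, SD 28). Test at a true ratio of 0.90 has 58.5% (41.5% remaining), same SD of 28. P = 0.403 and the rank ratio is 0.822. A product well inside the stated limits lies close to the rank limit.

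More generally, at CV 0.8 these are the true ratios of means at which the large-sample rank ratio equals 0.80:

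| Remaining lesions | Mean 45% | 55% | 65% |
|---|---|---|---|
| Lognormal, equal CV | 0.60 | 0.73 | 0.83 |
| Lognormal, equal SD | 0.74 | 0.82 | 0.88 |
| Gamma, equal CV | 0.49 | 0.66 | 0.78 |
| Gamma, equal SD | 0.70 | 0.80 | 0.87 |

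**Step 3: simulation of the rule.** Assumed: 200 / 400 per arm, equal arms, no site effects, 4,000 runs per cell (Monte Carlo SE at most 0.8 points). Each run computes Fieller on the original scale and replaces it by Fieller on ranks when residual skewness is below -2. CV is that of remaining lesions in the Reference arm. The table gives the percentage of trials passing at a true ratio of 0.80, per endpoint and per analysis set, at 200 / 400 per arm.

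| Case | Trigger fires, % | Mean 45% | 55% | 65% |
|---|---|---|---|---|
| Lognormal, equal CV, CV 0.8 | 78–80 / 91–92 | 44 / 74 | 18 / 30 | 3 / 2 |
| Lognormal, equal CV, CV 1.0 | 96 / over 99 | 64 / 91 | 37 / 57 | 8 / 8 |
| Lognormal, equal SD, CV 0.8 | 53–67 / 64–80 | 16 / 26 | 3 / 2 | 2 / 1 |
| Lognormal, equal SD, CV 1.0 | not tabulated | 28 / 47 | 4 / 4 | 0.6 / 0.2 |
| Gamma, equal CV, CV 1.0 | 38–47 | 32 / 44 | 28 / 42 | 18 / 28 |
| Gamma, equal SD, CV 1.0 | not tabulated | 11 / 18 | 6 / 6 | 4 / 5 |

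Milder cells change little: lognormal CV 0.5, 4–8%; gamma equal CV at CV 0.5, 5–6% and at CV 0.8, 6–10% (trigger 5–10%); gamma equal SD at CV 0.8, 5–6%. Fieller on the original scale gives 1.1–7.3% in every cell.

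For the stricter example, the pass rate at a true ratio of 0.90 is 38% / 34% under the rule and 82% / 97% on the original scale.

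**Step 4: both endpoints required** (lognormal, equal CV, CV 0.8, mean 45%; between-endpoint correlation 0 or 0.5). With both endpoints at 0.80, both pass in 21–25% / 53–56% of trials. With one at 0.80 and one identical, 37–39% / 72%. The original scale gives at most 7.2%. These figures omit the superiority tests and the second analysis set.

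**The case against.** - **The harm is conditional.** The SAP says percent change and never states the sign. If improvement were coded as negative, the tail would lie to the right and a trigger below -2 would almost never fire. Coding as reduction is inferred from Protocol 8.1.4 and the superiority hypotheses. Even so, the trigger may rarely fire: with gamma data it does so in at most 0.3% of runs at CV 0.5 and 5–10% at CV 0.8. This stands. It limits how often the defect matters, but does not supply a decision rule when it does.
- **The pass rates assume that 0.80 to 1.25 carries over.** True. If it does not, none of the rates apply and the defect is a missing rule for a co-primary endpoint.
- **The worst cells are chosen cells.** The 64% / 91% figure needs lognormal data, CV 1.0, a 45% mean and equal CV; with equal SD it falls to 28% / 47%. The stated test has only 20% / 62% power there for identical products, so a trial planned on the ratio might not be run at those inputs. Fair, but the lognormal, equal-CV cell with mean 45%, CV 0.8 and 400 per arm has 86% power on the original scale and 74% false equivalence under the rule.
- **Blacked-out text may hold a rank rule.** Parts of Protocol 8.1.4 and of the SAP's Superiority text are redacted, so this cannot be excluded. The SAP's Equivalent Efficacy text, where such a rule belongs, shows no redaction.
- **The switch is pre-specified and objective, and the SAP may add detail to the protocol.** Both true. Pre-specification removes analyst discretion; it does not make the rank analysis answer the stated hypothesis.

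**Conclusion.** The concern holds. As written, the triggered case either tests whether P lies between 0.389 and 0.611, or has no visible decision rule. Neither reading is the stated hypothesis. That conclusion is algebraic (for equal arms) and needs no simulation.

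The size is uncertain. Under the assumed distributions, spreads and sample sizes, the pass rate at a true ratio of 0.80 runs from 0.2% to 91% per endpoint and analysis set, against 1.1–7.3% for the stated test. The rule can also be much stricter than intended. Because equivalence is needed on both endpoints, the per-endpoint rates are upper bounds on error for the whole trial. How often skewness would fall below -2 cannot be learned from the documents, and at or above -2 the stated test is run unchanged. The rule should be fixed because it decides both co-primary endpoints and the correction is small.

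**What to change.** Delete the rank step from the equivalence analysis of both lesion types and state, for example: *Fieller's 90% confidence interval for the ratio of mean percent reductions on the original scale, from the ANOVA of Test and Reference with treatment and site, decides against 0.80 to 1.25 whatever the residual skewness. Skewness will be reported. Rank-based analyses are for sensitivity only.* This also fixes the sign convention and agrees with Protocol 8.1.4.

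If protection against skewness is wanted, pre-specify one method that keeps the same ratio and limits in all cases, such as a bootstrap 90% interval. That replaces the Fieller method named in the protocol, so the protocol would need to be aligned.

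The direct cost is one sentence removed and a short statement added before unblinding, with no new data or patients. The statistical cost is power where the SD is large relative to the mean. For identical products, per endpoint, at 200 / 400 per arm:

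| Case | Original scale, % | SAP rule, % |
|---|---|---|
| Lognormal, mean 45%, CV 0.8 | 46 / 86 | 89 / 99 |
| Lognormal, mean 45%, CV 1.0 | 20 / 62 | 95 / 99.9 |
| Lognormal, mean 55%, CV 0.8 | 90 / 99.7 | 96 / 100 |
| Lognormal, mean 55%, CV 1.0 | 70 / 96 | 97 / 100 |
| Gamma, mean 45%, CV 0.8 | 47 / 88 | 50 / 89 |
| Gamma, mean 45%, CV 1.0 | 15 / 62 | 46 / 78 |

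At a mean of 65% no power is lost. A bootstrap of the same ratio does not recover the loss (45% / 89% in the first row). The extra power under the rule is power for a different question, and it is largest in cells where false equivalence is also high. The sponsor should check the planned sample size against the original-scale test using its own variance assumptions.

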#### Superiority

Evaluation of superiority will be conducted separately for the Test versus Placebo products and for the Reference versus Placebo products comparing their difference in the percent change from baseline in the inflammatory lesion counts using ANOVA with treatment and site as fixed effects. If the mean percent change for an active treatment is greater and statistically different (two-sided,  $p < 0.05$ ) than that of the Placebo, then the active treatment will be considered superior to the Placebo. The compound hypothesis to be tested for superiority of test and reference over Vehicle is:

$H_0: \mu_T \leq \mu_V$  or  $\mu_R \leq \mu_V$  versus

$H_A: \mu_T > \mu_V$  and  $\mu_R > \mu_V$

Where  $\mu_T$ ,  $\mu_R$  and  $\mu_V$  are the mean percent change from baseline to Week 12 (Visit 4/Day 84) in inflammatory lesions counts for the test, the reference and the vehicle treatments, respectively.

. The null hypothesis is rejected when both p-values from the ANOVA are less than 0.05 (two-sided test). Rejection of the null hypothesis supports the conclusion of superiority of active product over the vehicle product for the primary efficacy variable.

[REDACTED]

The same analysis will be applied to the mean percent change from baseline in the non-inflammatory lesion count.

[REDACTED]

### 5.5.2 Secondary Endpoint

The secondary efficacy measure is the proportion of subjects with clinical success on the Investigator's Global Assessment (IGA) at Week 12 (Visit 4/Day 84), where success is defined as an IGA score that is at least 2 grades less than the baseline assessment.

#### Equivalent Efficacy

The Test treatment will be considered to be therapeutically equivalent to the Reference treatment if the 90% Wald confidence interval with Yates' continuity correction on the difference in their success proportions is contained within the interval of -20% to +20%.

#### Superiority

The proportion of subjects with clinical success for each active treatment will be compared separately between each of the active treatments and the Vehicle using two-sided,  $\alpha = 0.05$ , continuity-corrected Z-tests.

[REDACTED].

### 5.5.3 Additional Efficacy Variables

The following efficacy variables at Week 12 (Visit 4/Day 84) will be tabulated descriptively for both the PP and mITT populations: (1) inflammatory (papules and pustules) lesion counts, (2) non-inflammatory (open and closed) lesion counts, and (3) IGA.

## 5.6 Safety Variables and Analyses

#### Duration of Treatment and Medication Compliance

Number of applications, days of exposure, and compliance rate will be summarized by treatment group using descriptive statistics. For each subject, the overall duration of treatment (days) will be calculated using the following formula:

(Date of last application of study medication) - (Date of first application of study medication) + 1.

Medication compliance rate (%) will be calculated for each subject as follows:

(Total number of applications used) / (Expected number of applications) \*100%.

[REDACTED] For prematurely discontinued subjects, expected number of applications will be determined based on the expected number of applications by the time of discontinuation, i.e. the overall duration of treatment. Descriptive summaries of exposure and medication compliance rate will be provided by treatment group for the ITT subjects

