Title:	A Multi-Center, Double-Blind, Randomized, Vehicle-Controlled, Parallel-Group Study to Compare Perrigo Israel Pharmaceuticals, Ltd. Clindamycin Phosphate and Benzoyl Peroxide Topical Gel 1.2%/2.5% to Acanya® Topical Gel (Clindamycin Phosphate and Benzoyl Peroxide Gel 1.2%/2.5%), and Both Active Treatments to a Vehicle Control in the Treatment of Acne Vulgaris
Study Period:	12 weeks
Study Medication:	
 1. Clindamycin Phosphate and Benzoyl Peroxide Topical Gel 1.2%/2.5%, Perrigo Israel Pharmaceuticals, Ltd. 2. Acanya® Topical Gel (Clindamycin Phosphate and Benzoyl Peroxide Gel 1.2%/2.5%), Valeant Pharmaceuticals (Dow Pharmaceutical Sciences, Inc) 3. Vehicle of test product, Perrigo Israel Pharmaceuticals, Ltd.
Study Objectives:	To compare the safety and efficacy profiles of Perrigo Israel Pharmaceuticals, Ltd. Clindamycin Phosphate and Benzoyl Peroxide Topical Gel 1.2%/2.5% to Acanya® Topical Gel (Clindamycin Phosphate and Benzoyl Peroxide Gel 1.2%/2.5%) and to demonstrate the superior efficacy of the two active formulations over that of the vehicle in the treatment of Acne Vulgaris.
Study Design:	Subjects in this multi-center, double-blind, randomized, vehicle-controlled, parallel-group study will be admitted into the study only after written informed consent/assent (as applicable) has been obtained and after all inclusion/exclusion criteria have been met. Male and female subjects 12 years to 40 years of age, inclusive, with acne vulgaris will be eligible for enrollment.
Study Population:	██████████ healthy males and females, 12 to 40 years of age, inclusive, who meet the inclusion/exclusion criteria, will be enrolled to obtain ██████ per-protocol (PP) subjects.
Dosing:	Subjects will be randomized ██████ to either the test product, reference product or vehicle treatment group, respectively, and will apply ██████ to the affected areas of the face avoiding contact with the eyes, mouth, lips, inside and on angles of the nose, and mucous membranes once daily for 12 weeks.
Study Visits:	
Clinical Evaluations will be performed at:
 
 1. Visit 1/Day 1 (Baseline) 2. Visit 2/Week 4/Day 28 (± 4 days)(Interim) 3. Visit 3/Week 8/Day 56 (± 4 days)(Interim) 4. Visit 4/Week 12/Day 84 (± 4 days)(End of treatment/End study) 
Safety will be assessed by monitoring adverse events at each visit and at the Week 2/Day 14 (± 4 days) Telephone Contact.

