5.16 Subject/Treatment Compliance

Subjects will apply the medication to the affected areas of the face including the nose at approximately the same time once daily for 12 weeks. On Day 1, subjects will apply their initial dose of study medication at the study site under the supervision of study staff. Compliance will be determined from the diary card, in which the subject will be instructed to record all applications made or missed. On Week 2 Day 14/ (± 4 days), compliance will be assessed via telephone contact. The study co-ordinator will review Subject Instruction Sheet and Diary with the subject on the phone. The number of applications will be totaled by the study coordinator and recorded on the compliance page of the CRF. [REDACTED]

[REDACTED] [REDACTED] [REDACTED]. All used and unused pump bottles of study medication will be collected by the study site at appropriate visits or early termination.

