5.17 Discontinuation/Withdrawal of Study Subjects

Subjects may be removed from the study for any of the following reasons:

- The subject withdraws his or her consent for any reason.
- The subject's condition has worsened to the degree that the investigator feels it is unsafe for the subject to continue in the study.

- The subject's medication code is unblinded.
- Subject did not meet or no longer meets the entry criteria.
- An adverse event occurs for which the subject desires to discontinue treatment or the investigator determines that it is in the subject's best interest to be discontinued.
- The subject is lost to follow-up. The investigator will document efforts to attempt to reach the subject twice by telephone and will send a certified follow-up letter before considering that subject lost to follow-up. All attempts must be thoroughly recorded.
- The subject becomes pregnant during the course of the trial.
- [REDACTED]
- [REDACTED]

The reasons for a subject being discontinued will be documented in the case report form and the enrollment log.

If a subject is discontinued from the study for any reason, the Visit 4/ End of Study Visit/Early Termination Visit procedures should be completed and any outstanding data and study medication should be collected. Data, in addition to the reason for discontinuation and the date of removal, will be recorded on the End of Study Case Report Form.

[REDACTED]

[REDACTED]

[REDACTED]

[REDACTED]

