8.1 Statistical Analysis Plan

8.1.1 Analysing Populations

The following populations are defined for the purpose of analyses:

- Intent-to-Treat (ITT) (safety population): Any subject that was randomized received and used study medication.
- Modified Intent-to-Treat (mITT): Any subject, who met the inclusion/exclusion criteria, was randomized, received and used the study medication, and returned for at least one post-baseline efficacy assessment.
- Per Protocol (PP): Any subject:
 - Who met inclusion/exclusion criteria,
 - Who was randomized and received and used study medication.
 - Who met the protocol criteria for compliance [REDACTED] and [REDACTED]
 - Who completed Visit 4/Week 12 (End of Treatment/Early Termination Visit) within window [REDACTED]
 - Without significant protocol violations that could have interfered with the administration of the treatment or the precise evaluation of treatment efficacy.

A horizontal strip of black redaction bars, consisting of several thick black bars of varying lengths placed side-by-side, obscuring text or information.

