#### 4 Populations To Be Analyzed

Three subject populations are defined as follows:

- (1) An intent-to-treat (ITT) subject is any individual who: (a) was randomized into the study, received and (b) applied at least one dose of study medication;
- (2) A modified intent-to-treat (mITT) subject is any individual who: (a) met inclusion/exclusion criteria, (b) was randomized into the study, (c) received and applied at least one dose of study medication, and (d) had at least one post-baseline efficacy assessment for the two lesion types;
- (3) A per-protocol (PP) subject, consistent with the protocol, is one that: (a) met inclusion/exclusion criteria, (b) was randomized into the study, received and used study medication, (c) [REDACTED] (d) returned for Visit 4/ Week 12 (End of Treatment/Early Termination Visit) within the specified window ( $+/- 4$  days) and had data on lesion count, OR was discontinued early due to treatment failure [REDACTED]  
[REDACTED] and (e) took no concomitant medications prohibited by the protocol or had any other significant protocol violations, and

[REDACTED]  
[REDACTED]  
[REDACTED]  
[REDACTED]

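### Does ending the compliance denominator at the last application, for subjects who leave early, call for a change to SAP 5.6?

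*SAP*

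**What the plan says.** SAP 5.6, under Duration of Treatment and Medication Compliance, defines three things.

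- Duration of treatment in days: "Date of last application of study medication) - (Date of first application of study medication) + 1".
- Compliance rate: applications used divided by applications expected, times 100%.
- Expected applications for a prematurely discontinued subject: "determined based on the expected number of applications by the time of discontinuation, i.e. the overall duration of treatment".

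The sentence just before the rule for discontinuers is blacked out; the rule itself is readable. On use, the SAP says: "Descriptive summaries of exposure and medication compliance rate will be provided by treatment group for the ITT subjects".

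Protocol 5.16 sets once-daily application and takes compliance from the diary card, "in which the subject will be instructed to record all applications made or missed". Protocol 5.17 collects a separate end date for anyone who leaves: data, "in addition to the reason for discontinuation and the date of removal, will be recorded on the End of Study Case Report Form".

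A compliance condition also appears in the per-protocol definition in Protocol 8.1.1 ("Who met the protocol criteria for compliance"), but its content is redacted. SAP section 4 lets a subject into that population without an in-window Week 12 visit if the subject "OR was discontinued early due to treatment failure".

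**The concern.** The SAP sentence treats two dates as one. The time of discontinuation would naturally be read as the date of removal in Protocol 5.17, yet the duration it is equated with stops at the last application. The two differ whenever a subject stops applying before leaving the study.

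The consequence is one-sided. Missed days before the last application lower the rate, but a final run of missed days cannot, although the diary is meant to capture missed applications. Someone who applies faithfully for four weeks, stops without telling the site and is removed four weeks later scores 100%. Clinic visits are four weeks apart with one telephone contact at Week 2, so such gaps are foreseeable.

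If this mattered, the ITT compliance summary would look better than actual use. If the redacted per-protocol criterion used the same rate, an early treatment failure might also pass a compliance threshold that the subject should have failed.

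**Working it through.** The documents give no compliance figure, dropout rate or readable sample size for this point, so there is no stated figure to reproduce. The check applies the SAP's formulas directly.

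**Inputs.** First application is on Day 1 at the site (Protocol 5.11), with one expected application per day (Protocol 5.16). Visit 2 falls on Day 28 ± 4, so Day 24 to 32. The Protocol synopsis lists the next visit as "Visit 3/Week 8/Day 56 (± 4 days)(Interim)", so Day 52 to 60.

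**Formulas.** Let n be applications used, L the day of the last application and D the day of removal.

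- SAP rate = n / L
- Rate to removal = n / D
- Ratio of the two = D / L, which is at least 1 because D cannot precede L

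**Illustrations.** The first three rows assume a last application on the Visit 2 day and removal on the Visit 3 day. The last three are free choices.

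| L | D | n | SAP rate n/L | Rate to removal n/D | Difference (points) |
|---|---|---|---|---|---|
| 28 | 56 | 28 | 100% | 50% | 50 |
| 24 | 60 | 24 | 100% | 40% | 60 |
| 32 | 52 | 32 | 100% | 61.5% | 38.5 |
| 20 | 50 | 15 | 75% | 30% | 45 |
| 47 | 50 | 47 | 100% | 94% | 6 |
| 50 | 50 | 50 | 100% | 100% | 0 |

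**Effect on an arm mean.** Shift = share of the arm affected × difference. The shares are assumed.

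- Difference of 50 points: 0.02 × 50 = 1.0; 0.05 × 50 = 2.5; 0.10 × 50 = 5.0 points.
- Extremes of the Visit 2 to Visit 3 pattern: 0.02 × 38.5 = 0.8 and 0.10 × 60 = 6.0 points.
- Short gap: 0.02 × 6 = 0.12 points.
- No gap: zero.

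The direction is fixed by the formulas. The size depends entirely on how many subjects have a gap and how long it is, and the documents give neither.

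**The opposite error.** Suppose a subject withdraws consent on Day 20 having missed nothing, and removal is dated at an early-termination visit on Day 30. The SAP rate is 20/20 = 100%. The rate to removal is 20/30 = 67%, although the subject missed no application while taking part.

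**Where the rate goes.**

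- Efficacy is analysed in the PP and mITT populations (Protocol 8.1.2). The compliance summary is for ITT and is descriptive. No visible test, confidence interval or equivalence conclusion uses it.
- The same part of SAP 5.6 summarises number of applications and days of exposure by arm. SAP 5.4 tabulates disposition and reason for discontinuation by arm. The adverse event part of SAP 5.6 lists events that led to interruption or discontinuation.
- Early leavers other than treatment failures generally fail the in-window Week 12 condition in SAP section 4, whatever their compliance rate. For treatment failures, Protocol 5.12.6 ties discontinuation to the investigator's own assessment, so only a self-chosen stop before that assessment would matter.

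**The case for a change.** The strongest case for a change is that a figure called the medication compliance rate, reported for ITT subjects, should reflect whether subjects took what they were meant to take. It should not reset its horizon to the point at which they gave up. Short exposure shown alongside does not correct a 100% entry, and it does not say whether the stop was ordered or how long the subject stayed in the study untreated. The date of removal is already collected, so a change would take one or two sentences. Reading discontinuation as stopping treatment makes the SAP sentence consistent but still leaves trailing missed days uncounted.

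Most of this stands as description. The two dates can differ, the wording blurs them, and the rate is blind to the last untreated stretch.

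What does not stand is the step to calling the rate inflated. That word assumes the target is adherence up to removal, and neither document sets that target. The visible text also does not say whether the date of removal is the day of the decision, the day of the final visit or an administrative date. A denominator run to that date would need separate rules for ordered stops, withdrawals, loss to follow-up and unreturned diaries. Without them it would score some proper withdrawals as non-compliance. The per-protocol argument may be right, but it rests on a criterion that cannot be read.

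**Conclusion.** No change to the plan is needed. For early discontinuers, SAP 5.6 measures compliance up to the last application, and it says so through its own definition of duration. That measure can exceed one run to removal by a wide margin for an individual (100% against 40% to 61.5% in the Visit 2 to Visit 3 illustration). At arm level it shifts the mean by 0.8 to 6.0 points if 2% to 10% of subjects follow that pattern, by much less for short gaps, and not at all where subjects apply until they leave. These shares and gaps are assumptions.

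The visible consequence is confined to one descriptive line in a set of tables that also shows exposure, applications and disposition. Which date should end the denominator is a choice on which competent statisticians differ, since each option misstates some subjects. The loose equation of the two dates is something an analyst settles when programming and footnoting the table, by noting that the rate runs to the last application.

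The conclusion assumes that the redacted per-protocol compliance criterion does not turn on this rate for early treatment failures. If it does, the effect is limited to those treatment failures who stopped applying of their own accord before the investigator's decision.
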